9.6.1.2. Secondary Efficacy Endpoints

The secondary efficacy endpoints will be analyzed based on the FAS. The 2-sided p-values and 2-sided 95% CIs will be reported for treatment difference between each of the CC-90001 treatment groups versus placebo.

The binary endpoints will be summarized using counts and percentages, and the treatment comparison will be performed similarly as the primary endpoint using the CMH test.

The continuous efficacy endpoints will be summarized using mean, standard deviation (SD), median, minimum, maximum, and number of observations analyzed. For all continuous efficacy endpoints, the treatment comparisons will be performed using a mixed model of repeated measures (MMRM) as the primary analysis method of the secondary efficacy endpoints. The MMRM will use the change from baseline as the dependent variable and will include dose, time on treatment, and their interaction as fixed effects covariates. The model will also include the stratification factors (fibrosis stage (Stage 2/ Stage 3) and presence of Type 2 DM (yes/no), at randomization) and corresponding baseline value as fixed effects covariates. Time will be treated as a categorical variable in the MMRM and will be considered as a repeated effect. All post-baseline measurements up to Week 52 will be included in this analysis with no imputation of missing data other than that inherent in the MMRM. Within-group least-squares (LS) means and the associated standard errors (SEs) and 2-sided 95% CIs, treatment differences in LS means and the associated 2-sided 95% CIs and 2-sided p-values will be derived from the MMRM.

As a sensitivity analysis method for all secondary continuous efficacy endpoints an analysis of covariance (ANCOVA) model will be used. The ANCOVA model will use the change from baseline as the dependent variable, treatment group as a fixed factor, and the baseline value and stratification factors (fibrosis stage (Stage 2 /Stage 3) and presence of Type 2 DM (yes/no), at randomization) as covariates. Within-group least-squares (LS) means and the associated standard errors (SEs) and 2-sided 95% CIs, treatment differences in LS means and the associated 2-sided 95% CIs and 2-sided p-values will be derived from the ANCOVA model.

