- ^d Visit 5 Week 8 and Visit 7 Week 16 will be remote visits. Central laboratory tests, target physical examination, vital sign and weight will not be performed during these remote visits. However, if laboratory tests and/or physical examination is needed based on the Investigator's clinical judgement, an unscheduled visit should be performed at the investigational site. Urine pregnancy test kits will be provided to the subjects at Visit 4 Week 4 and Visit 6 Week 12. At Visit 5 Week 8 and Visit 7 Week 16 subjects will perform urine β -hCG test at home. IP will be dispensed at Visit 4/Week 4 and Visit 6/Week 12 for these 2 visits.
- ^e Urine pregnancy test will be performed to assess subject eligibility prior to the first administration of IP if a serum pregnancy test was not obtained within 72 hours prior to dosing (negative results required for IP administration).
- ^f Subjects who do not have a historical biopsy will undergo a liver biopsy procedure for study eligibility. The independent histopathologists will review the liver biopsy specimens to assess whether the subject meets the histological inclusion criteria. Screening liver biopsy will serve as the Baseline assessment. Subjects who discontinue after Week 20 and before Week 52 will undergo a liver biopsy procedure at ET Visit. IP should be stopped 7-10 days prior to Week 53 or ET Visit biopsy and restarted 7 days after biopsy at Week 54 if subjects participate in the active treatment phase.

^j First dose of IP should be administered at the investigative site.

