9.6. Efficacy Analysis

9.6.1. Efficacy Evaluation for the Placebo-controlled Phase (Weeks 0 to 52)

For the Placebo-controlled Phase (Weeks 0 to 52), the analyses for efficacy endpoints will be based on the FAS. Statistical comparisons will be made between each of CC-90001 treatment groups versus placebo. All statistical tests will be at the two-sided 0.05 significance level and the corresponding p-values and 95% confidence intervals (CIs) will be reported. No adjustment for multiple comparisons will be made in this phase 2 study. The nominal p-values will be reported to give an indication of the strength of association regarding the treatment differences.

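### The MMRM for continuous secondary endpoints gives baseline one slope for all visits, which can cost some precision at Week 52; a baseline-by-visit term is a cheap improvement

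*Combined protocol and SAP*

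**What the plan says.** Section 9.6.1.2 makes an MMRM on change from baseline the main analysis of the continuous secondary endpoints, which in Table 2 are AST, ALT, GGT and the lipids. The model "will include dose, time on treatment, and their interaction as fixed effects covariates". It also has the two stratification factors and the "corresponding baseline value as fixed effects covariates". On time it says: "Time will be treated as a categorical variable in the MMRM and will be considered as a repeated effect". On data: "All post-baseline measurements up to Week 52 will be included in this analysis". No baseline-by-visit term is listed, and no covariance structure is given.

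The sensitivity analysis for the same endpoints is an ANCOVA with the baseline value as a covariate. The visit at which it is fitted is not stated. Section 9.1 describes Section 9 as an outline and leaves details to a separate SAP, which is not in the text reviewed.

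Section 9.6.1 sets the inferential standing of these results: "All statistical tests will be at the two-sided 0.05 significance level" and "No adjustment for multiple comparisons will be made in this phase 2 study".

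**The concern.** When the outcome is change from baseline, the right baseline slope at a visit is the regression slope of that visit's value on baseline, minus 1. If early values track baseline closely and late values less so, the slope becomes steeper (more negative) with time. A single slope must compromise. Under an unstructured covariance, generalised least squares sets it largely from the visits where change has the least residual variance, which are the early ones. The Week 52 contrast then gets too little baseline adjustment.

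At stake is the width of the Week 52 intervals for liver biochemistry and lipids. The MMRM and a Week 52 ANCOVA could also differ for a reason unrelated to missing data.

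**Working it through.** **No figure to reproduce.** The protocol gives no SD, correlation, effect size or power for any continuous endpoint. Everything below is conditional on assumed correlations.

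**Inputs from the protocol.** Arms of 60, 60 and 60, and 10-15 at 100 mg (Section 9.3). From Table 3, chemistry is drawn after baseline at Weeks 1, 4, 12, 20, 24, 30, 36, 42, 48 and 52. Weeks 8 and 16 are remote: "Central laboratory tests, target physical examination, vital sign and weight will not be performed during these remote visits". That leaves 10 visits.

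**Assumptions.** Unit SD at every visit, unstructured covariance, complete data, no effect of the stratification factors.

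**Formulas.** Let ρ_t be the correlation of visit t with baseline, b_t = ρ_t − 1 the correct slope on change, and W the residual covariance given baseline (W52 = 1 − ρ52²). The single slope tends to g = 1′W⁻¹b / 1′W⁻¹1. For arms of n1 and n0:

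- Week 52 variance with visit-specific slopes: W52 (1/n1 + 1/n0)
- Week 52 variance with a single slope: [W52 + (b52 − g)²] (1/n1 + 1/n0)
- Ratio: 1 + (b52 − g)² / W52

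**Worked case.** Take correlation at lag L weeks of 0.5 + 0.3·exp(−L/20). Then ρ52 = 0.522, b52 = −0.478, W52 = 0.727 and g = −0.311. The gap is 0.167, and the ratio is 1 + 0.0278/0.727 = 1.038.

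**Range over the 10 visits**

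| Assumed correlation at lag L | b52 | g | Ratio |
|---|---|---|---|
| Constant, 0.5 or 0.7 | −0.50, −0.30 | same as b52 | 1.00 |
| 0.7 × 0.8^(L/52): noisy, slow decay | −0.440 | −0.352 | 1.01 |
| Decay 0.8 to floor 0.5 | −0.478 | −0.311 | 1.04 |
| Decay 0.7 to floor 0.3 | −0.670 | −0.472 | 1.04 |
| Decay 0.8 to floor 0.4 | −0.570 | −0.344 | 1.06 |
| Decay 0.9 to floor 0.6 | −0.378 | −0.181 | 1.06 |
| 0.9 × 0.6^(L/52): damped AR | −0.460 | −0.165 | 1.12 |
| Pure AR(1), 0.8 at 52 weeks | −0.200 | −0.005 | 1.10 |
| Pure AR(1), 0.6 at 52 weeks | −0.400 | −0.015 | 1.23 |
| Pure AR(1), 0.4 at 52 weeks | −0.600 | −0.033 | 1.38 |

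In the decay-to-floor rows the single slope makes 48-70% of the needed adjustment (g/b52). In the pure AR(1) rows it makes 3-5%.

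**Only Weeks 24 and 52 measured.** The same formula gives 1.000-1.003 for constant or decay-to-floor patterns, and 1.04 for AR(1) falling to 0.6.

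**What a ratio means.** At 1.12 the SE rises by √1.12 − 1 = 6%. A comparison with 80% power under visit-specific slopes would have Φ(2.802/√1.12 − 1.960) = Φ(0.687) = 75%. At 1.04-1.06 it would have 78%, and at 1.23 it would have 71%.

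**Simulation check.** Arms 60/60/60/15, 4000 trials per pattern, with the comparison at 60 vs 60. Variance ratios were 0.996 (constant 0.5), 1.033 (0.8 to 0.5), 1.052 (0.8 to 0.4), 1.062 (0.9 to 0.6) and 1.221 (AR(1), 0.6). Mean error was at most 0.006 SD and matched the visit-specific model. Type I error of the single-slope model was 0.049-0.052.

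**Imbalance and precision are one effect.** In the patterns with decay, the simulated Week 52 estimate moved by 0.17-0.38 SD per 1 SD of baseline imbalance, against at most 0.015 with the interaction. Chance imbalance at 60 vs 60 has SD √(2/60) = 0.183, so the typical leftover shift is 0.183 × 0.17 = 0.03 to 0.183 × 0.38 = 0.07 SD. Averaged over randomisation, that shift is exactly the (b52 − g)² term already in the variance.

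**The case against.** The strongest reply is that the loss cannot be shown from the documents and may be trivial. The Amendment 4 justification says that ALT and AST fluctuate over short periods. Noise of that kind lowers the Week 1 correlation too and flattens the slopes (ratio 1.01 above). Section 6.5.3 requires fasting only at Baseline, Week 24 and Week 52 or early termination, so for triglycerides the correlation need not fall steadily. The printed chemistry panel does not list GGT, and the partly redacted metabolic sample is drawn after baseline only at Weeks 24, 52 and early termination. The 10-visit schedule may therefore not apply to every endpoint. All of this stands, and it is why the size is given as a range starting at zero.

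Two further replies stand in part. Model detail is deferred to the SAP, which may already have the term; but Section 9.6.1.2 lists its fixed effects and writes an interaction where one is wanted, so the stated model is the single-slope one. An ANCOVA fitted at Week 52 has its own slope; but it is only the sensitivity analysis, and its visit is not stated.

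A reader might infer more than the documents support:

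- **Bias or inflated type I error.** The calculations show neither under randomisation.
- **Special harm to the 100 mg arm.** The absolute shift is larger with 10-15 subjects, but the variance ratio does not depend on n, so relative to its own SE that arm is no worse off. Its recruitment ended at Amendment 4 while placebo continued. That is a separate question, and no baseline data are given to show a systematic difference.
- **Dose fitted as a number.** The section promises within-group LS means and each group against placebo, so dose is evidently categorical.

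**Conclusion.** The point holds as a minor, conditional improvement. As written, one baseline slope serves all visits. If the baseline correlation falls over 52 weeks, the Week 52 contrast is under-adjusted. Its variance is then about 0-12% larger in most assumed patterns, and larger still only where decay is AR(1) or close to it (up to 38% at a 52-week correlation of 0.4). With constant correlation there is no loss.

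This rests on the assumed correlations, equal SDs, unstructured covariance and complete data; dropout and skewed laboratory values were not covered by this range. The stated analysis remains valid. The affected endpoints are secondary with nominal p-values, and the CMH analysis of the primary endpoint is untouched.

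**What to change.** In Section 9.6.1.2, add the interaction of baseline value with categorical visit to the MMRM for the continuous secondary endpoints, and state the same model in the SAP. The Week 52 contrast then uses its own baseline slope, as a Week 52 ANCOVA would.

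The cost is one line of text and no new data. With 10 visits there are 10 slopes in place of one, so nine extra parameters per endpoint on about 195 subjects. If the slopes are truly equal, the simulated ratio of 0.996 puts the price at about 0.4% in variance: negligible, though not nil. The change is best made before unblinding.

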9.6.1.4. Dose-Response modelling

The method for dose-response modeling called MCP-Mod (Section 9.3 and Bretz, 2005) will be applied to the primary endpoint and select additional endpoints. It will allow for an evaluation of which dose-response curves are the best fit given the 52 weeks data and a potentially more accurate estimation of the MED. In this study, MCP-Mod delivers at least 80% power to ascertain a dose response with type I error rate of 5% (c.f. section 9.3). Under the scenarios evaluated, it has high probability to determine the MED. The details will be further elaborated in the Statistical Analysis Plan.

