9.3. Sample Size and Power Considerations

The estimated improvement on ≥ 1 fibrosis score in Stage 3 subjects of 45% for CC-90001 group and 20% for the placebo group is based on a Phase 2 study of selonsertib, which reported a 23% treatment difference (43% in the selonsertib 18 mg group versus 20% in the simtuzumab group-a compound that was not demonstrated to be effective for NASH with a treatment response similar to placebo from other clinical trials) (Loomba, 2018; Neuschwander-Tetri, 2015).

With the above assumed treatment responses for the primary endpoint between the highest CC-90001 dose group and the placebo, and further assuming a similar treatment effect in Stage 2 subjects, the sample size of 60 for the placebo, 200 mg, and 400 mg treatment group and an expected sample size of 10-15 for the 100 mg treatment group provides the ability to determine a dose response with 80% power, and 5% type I error rate.

This sample size was estimated using the multiple comparison and dose-response modeling (MCP-Mod) procedure and considering five dose-response models (linear, log-linear, two Emax shapes and logistic) (Bretz, 2005; R-package “MCPMod”, version 1.0-10.1 August 5, 2017).

Determination of the minimum effective dose (MED) will follow the MCP-Mod method (Bretz, 2005). Based on this method, a dose will be considered as MED if it satisfies the following two criteria: (i) the response rate of the dose is greater than that of placebo by a clinically relevant treatment difference (Δ), and (ii) the lower confidence bound of the response rate of that dose has to be greater than that of placebo. Simulations were run to assess the sensitivity to determine the MED with examples of Δ and 80% confidence intervals of the response rates.

Table 5: Probability of Each Dose to Be Considered the MED for Various Response Scenarios and Delta

Scenarios	Response Rate			MED Probability ^c		
	100 mg	200 mg	400 mg	Dose (mg)	$\Delta=0.10$	$\Delta=0.15$
1 ^b	0.325 (50% of emax ^c)	0.45	0.45	100	52.80%	44.18%
				200	37.06%	39.84%
				400	0.44%	6.30%
				MED not identified	9.70%	9.68%
2	0.2625 (25% of emax)	0.3875 (75% of emax)	0.45	100	30.38%	20.06%
				200	55.86%	49.30%
				400	1.54%	18.62%
				MED not identified	12.22%	12.02%
3	0.25 (20% of emax)	0.325 (50% of emax)	0.45	100	17.48%	8.04%
				200	62.06%	39.30%
				400	4.26%	36.96%
				MED not identified	16.20%	15.70%

Abbreviations: PBO = placebo; MED = minimum effective dose.

Response Rate for PBO=0.2

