^b Response rate at the 100 mg dose closer to response rate at the next dose than the other scenarios.

^c emax is the assumed maximum effect of 45%-20%.

^c With assumed sample size being 15 subjects for the 100 mg dose group and 60 subjects otherwise.

Δ clinically relevant treatment difference.

Based upon these assessments, the planned sample size provides high sensitivity to determine a MED when a range of response rates and clinically significant effects are assumed. Details of the simulations and estimations will be further elaborated in the Statistical Analysis Plan. In addition to considering MED purely based on efficacy in response rates, the overall determination of the MED will also account for additional efficacy and safety endpoints.

Therefore, approximately 180 subjects will be randomized in a 1:1:1 ratio to receive CC-90001 (200 mg QD, 400 mg QD) or placebo. Randomization will be stratified by liver fibrosis stage (Stage 2/Stage 3) and by the presence of Type 2 DM (yes/no). Approximately 60 subjects with

Stage 2 or Stage 3 fibrosis will be enrolled per arm. To ensure enrollment of a suitable number of subjects with Stage 3 fibrosis, up to 15 subjects with Stage 2 fibrosis may be enrolled per arm. Randomization to one stratum will be halted once the enrollment target is achieved for that stratum.

Subjects who have been randomized to the 100 mg QD treatment arm prior to implementation of Protocol Amendment 4 will be included in the study populations as appropriate. It is expected that randomization into the 100 mg dose group will be stopped at approximately 10-15 randomized subjects at time of implementation of Protocol Amendment 4. Thus, a total of approximately 195 subjects will participate in the study.

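### Does section 9.6.1.4 overstate how often MCP-Mod will determine the minimum effective dose?

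*Combined protocol and SAP*

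**What the plan says.** Section 9.6.1.4 first gives MCP-Mod at least 80% power to detect a dose response at a 5% type I error rate, citing section 9.3. It then adds: "Under the scenarios evaluated, it has high probability to determine the MED". No number is attached, and details are left to the SAP.

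Section 9.3 defines the MED by a rule: "a dose will be considered as MED if it satisfies the following two criteria". The first is that "the response rate of the dose is greater than that of placebo by a clinically relevant treatment difference" (Δ). The second is that the dose's lower confidence bound lies above placebo. The simulations used example values of Δ (0.10 and 0.15) and 80% confidence intervals. They are introduced with "Simulations were run to assess the sensitivity to determine the MED" and reported under "Table 5: Probability of Each Dose to Be Considered the MED for Various Response Scenarios and Delta". For each scenario and Δ, the table gives the probability that 100, 200 or 400 mg is named, and the probability that none is.

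Section 9.3 concludes that "the planned sample size provides high sensitivity to determine a MED when a range of response rates and clinically significant effects are assumed". It defers the rest: "Details of the simulations and estimations will be further elaborated in the Statistical Analysis Plan". It also says that "the overall determination of the MED will also account for additional efficacy and safety endpoints".

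**The concern.** To determine the MED can mean two things: that the procedure names some dose, or that it names the correct one. In a dose-finding trial the second matters more, and the sentence does not say which is meant. It follows directly on a power statement of at least 80%, so a reader may suppose that the correct dose is found about that often.

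Table 5 does not support that. Its individual dose probabilities are mostly near or below one half, and at Δ = 0.15 in scenarios 1 and 3 the most likely selection is a dose whose assumed effect falls short of Δ. Someone relying on section 9.6.1.4 alone could expect more of the procedure's dose choice than the sponsor's own simulations show.

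**Working it through.** **Inputs (all from section 9.3, Table 5 and its footnotes).** Placebo rate 0.20. Assumed rates at 100/200/400 mg: scenario 1, 0.325/0.45/0.45; scenario 2, 0.2625/0.3875/0.45; scenario 3, 0.25/0.325/0.45. Subtracting 0.20 gives effects of 0.125/0.25/0.25, 0.0625/0.1875/0.25 and 0.05/0.125/0.25. Sample sizes are 15 at 100 mg and 60 in each other arm.

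**Step 1: does the table hang together?** In each column the three dose probabilities and the not-identified probability should sum to 100%. For scenario 1, Δ = 0.10: 52.80 + 37.06 + 0.44 + 9.70 = 100.00. The other five columns also sum to 100.00, so each simulated trial ends with exactly one named dose or none.

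**Step 2: probability that some dose is named** = 100 − not identified. For scenario 3, Δ = 0.10: 100 − 16.20 = 83.80.

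**Step 3: probability that the correct dose is named.** The protocol labels no dose as correct. Applying the first criterion to the assumed rates, take the lowest study dose whose effect exceeds Δ. No effect equals 0.10 or 0.15, so there are no ties. The conditional figure is that cell divided by the step 2 result, for example 36.96 / 84.30 = 43.84%.

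| Scenario, Δ | Some dose named, % | Lowest dose with effect > Δ | That dose named, % | Same, given a dose is named, % | A lower dose named, % |
|---|---|---|---|---|---|
| 1, 0.10 | 90.30 | 100 mg | 52.80 | 58.47 | 0 |
| 1, 0.15 | 90.32 | 200 mg | 39.84 | 44.11 | 44.18 |
| 2, 0.10 | 87.78 | 200 mg | 55.86 | 63.64 | 30.38 |
| 2, 0.15 | 87.98 | 200 mg | 49.30 | 56.04 | 20.06 |
| 3, 0.10 | 83.80 | 200 mg | 62.06 | 74.06 | 17.48 |
| 3, 0.15 | 84.30 | 400 mg | 36.96 | 43.84 | 47.34 |

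The last entry is 8.04 + 39.30. Some dose is named in 83.80–90.32% of trials. The dose taken as correct is named in 36.96–62.06%, with a mean of 296.82 / 6 = 49.47%.

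**Step 4: how far does this depend on the choice of correct dose?** MCP-Mod fits curves, so an estimated MED can fall between study doses. Interpolating the assumed effects linearly (an assumption), the dose at which the effect reaches Δ is d_low + (Δ − e_low) / (e_high − e_low) × (d_high − d_low).

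- Scenario 1, Δ = 0.15: 100 + 0.025 / 0.125 × 100 = 120 mg.
- Scenario 2, Δ = 0.10: 100 + 0.0375 / 0.125 × 100 = 130 mg.
- Scenario 3, Δ = 0.15: 200 + 0.025 / 0.125 × 200 = 240 mg.

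Rounding to the nearest study dose instead of upward changes the benchmark in these three columns, to 100, 100 and 200 mg. The range becomes 30.38–62.06%. The lower limit moves with the convention. The upper limit cannot, because 62.06% is the largest single-dose entry in the table.

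**Step 5: is the not-identified row credible?** An MCP-Mod simulation was run with the planned sample sizes, a two-sided 5% test and 3000 runs per scenario. Its shape parameters were assumed, since the protocol gives none: log offset 4, Emax ED50 25 and 100, logistic ED50 200 with slope 40. Dose-response power was 91.4/88.1/84.4% for scenarios 1/2/3. No MED was found in 8.6/11.9/15.6%, against 9.70/12.22/16.20% in Table 5 at Δ = 0.10 and 9.68/12.02/15.70% at Δ = 0.15. All are within about 1.1 points. In that simulation the failures equal 100 minus the power (100 − 91.4 = 8.6, and so on), so finding no MED is in effect failing the dose-response test.

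The split between doses was not reproduced: scenario 1, Δ = 0.10, 100 mg gave 70.9% against 52.80%. The split depends on shape parameters and a dose-assignment rule that the documents do not state, so the mismatch is no evidence against Table 5.

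**The case for a change.** The best case for rewording is that the sentence asserts an operating property without defining it, and the property that matters most for dose selection does not merit the word high. Table 5 prints the cells but marks no dose as correct, so the reader has to derive correct selection. At Δ = 0.15 in scenarios 1 and 3 the leading selection misses Δ (44.18% against 39.84%, and 39.30% against 36.96%). One sentence would settle it at no cost, and leaving details to the SAP does not define a claim already made in the protocol.

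Part of this stands. The event is undefined, and under any assignment of the correct dose the chance of naming it is at most 62.06%.

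The rest does not amount to a misstatement. The rule-based definition in section 9.3 and the table's not-identified row both point to the reading on which the sentence is true. The two awkward columns turn on an effect of 0.125 against a Δ of 0.15, a shortfall of 0.025, and on rounding up to a study dose, which the criterion's per-dose wording favours but the documents do not confirm for the simulation. Writing a range such as 37–62% into the protocol would fix a definition of the correct MED that may not match the one the simulation used.

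**Conclusion.** No change to the plan follows. This is an undefined event in a summary sentence, and section 9.3 supplies both the definition and the numbers. On the natural reading, that some dose meets the MED criteria, the probability is 83.80–90.32% and calling it high is fair. On the stricter reading it is 36.96–62.06% if estimates are rounded up to a study dose and 30.38–62.06% if rounded to the nearest. Both stricter ranges rest on a definition of the correct dose that the protocol does not give; only the ceiling of 62.06% is free of it.

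No Table 5 figure is shown to be wrong. Rewording would leave the dose-response test, the sample size, the MED rule and the primary analysis as they are. The MED decision is also not mechanical, because section 9.3 brings in other efficacy and safety endpoints. The simulation details already promised for the SAP are the place for correct-dose selection, reported with the simulation's own definition and assignment rule. That is ordinary completion of a deferred detail.
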